After enrollment, the Patient-Reported Outcomes Measurement Information System (PROMIS) Global Measure of Health v1.2 questionnaire for (pre-morbid health) will be administered to the patient or their LAR depending on the patient's ability to complete the form. At the last follow-up visit the patient or LAR will complete the Stroke Impact Survey. Additionally, the Sunnybrook Neglect Assessment Procedure will be administered to the patient on day 1 of the study, on transfer from the ICU or discharge from the hospital and at 30 days after the hemorrhage.³¹ If the patient is assessed as not having neglect at the time of enrollment or is found not to have neglect as measured by the assessment procedure then they will not have to complete this measure at subsequent time points.

The intervention group will receive two CE sessions per day after randomization with a unit owned cycle (Reck Motomed Letto, Germany). Sessions will be held at least 2 hours apart to allow for patient rest and activities of patient care. The clinician will set the device to an automatic program where passive cycling will be initiated and the device will provide resistance if the patient attempts to actively cycle. Vital signs (e.g., heart rate, blood pressure, pulse oximetry, intracranial pressure) will be monitored continuously by a study team member present at the bedside during the CE session, if an

Figure 1: Supine cycle ergometer

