Usual care in the NCCU consists of evaluation and treatment by physical and occupational therapists assigned to the neurosciences service when an order for evaluation and treatment is entered by medical providers. Patients may be seen up to 5 times per week depending on their level of participation and intensity of therapy required, however many patients with sICH particularly those in coma are treated by therapists 2 times per week. Nursing staff in the NCCU provide passive range of motion and progressive a patient's mobility from supine to upright positioning, sitting at the side of bed, transferring to chair, lift assisted transfer to chair and ambulation as the patient's condition allows. All usual care activities will be recorded by the study team via extraction from the medical record. Usual care during the pandemic is similar to the care described above however, due to resource constraints it is possible that care focused on mobility and recovery was reprioritized in order to provide acute and intensive care for other patients.

Table 1. Study Activities Schedule for the intervention and prospective control group

	Admission day 1-2	Study day 1 = hospital day 3	Study day 2 = hospital day 4	Study day 3 = hospital day 5	Study day 4 = hospital day 6	Study day 5 = hospital day 7	Study day 6 = hospital day 8	Study day 7 = hospital day 9	Day of ICU transfer	30 days after hemorrhage (-10, +30 days)
Screening, Inclusion/Exclusion, Consent	X									
Intervention and monitoring										
Cycle ergometry 20 minute sessions (twice each study day)		XX								
Vital signs (BP, HR, RR, SpO ² , ICP)		X	X	X	X	X	X	X		
Pain scores		X	X	X	X	X	X	X		
Physiologic outcomes for the intervention and control groups										
Blood draw (IL1- β , IL-6, TNF- α , IL-10, CRP, BDNF)		X		X				X		
Saliva sample for cortisol		X		X				X		
CSF sampling, if a external ventricular		X		X				X		

drain is in place										
Outcome measures										
Medical Research Council Sum Score (strength testing) ²¹		X		X				X	X	X
Grip strength		X		X				X	X	X
Modified Rankin scale score	X								X	X
Barthel Index ¹²									X	X
Sunnybrook Neglect Assessment Procedure (SNAP) ³¹		X							X This battery will only be completed if the patient was found to have neglect on the initial assessment.	X This battery will only be completed if the patient was found to have neglect on the initial assessment.
Questionnaires										

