Promis Global Measure of Health v1.2 to patient or legally authorized representative (LAR)		X								
Stroke										X

Impact Survey to patient or LOR										
---------------------------------	--	--	--	--	--	--	--	--	--	--

b. Study duration and number of study visits required of research participants.

The study will enroll patients for approximately two years. Each patient will receive study interventions or procedures depending on group assignment for 7 days, assessment of motor function and physical/cognitive functioning on transfer from the NCCU or 1 day after the last study day if the patient completed study activities outside of the NCCU and 30 days (-10 days, +30 days) after occurrence of sICH. We will allow a 30 day time period in which to contact the patient if they are not able to be contacted on the 30th day for a total study period of 60 days. If a patient is seen in clinic prior to the 30 day period after the hemorrhage, follow-up assessments will be performed at that time. The stroke service currently collects a modified Rankin score for all ischemic and hemorrhagic stroke patients at 90 days via phone as a standard of care. We will record this value for all patients in this study. If a patient is not scheduled for an in-person visit after discharge, only the 90 day modified Rankin scale will be collected as an outcome measure.

c. Blinding, including justification for blinding or not blinding the trial, if applicable.

This pilot trial cannot be blinded because of the use of the supine cycle ergometer which is a large piece of equipment introduced into the patients' rooms in the intervention group twice per day during the initial study period, however outcome measures at NCCU transfer and 30 days will be obtained by a study team member blinded to the participant's group assignment.

d. Justification of why participants will not receive routine care or will have current therapy stopped.

Current therapy will not be stopped. Participants will receive the study intervention in addition to usual care.

e. Justification for inclusion of a placebo or non-treatment group.

In order to detect a signal of cytokine modulation with the intervention regimen of supine cycle ergometry, a control group not receiving the intensive intervention regimen is necessary for comparison.

f. Definition of treatment failure or participant removal criteria.

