If a patient meets the following stopping criteria on >2 consecutive sessions the patient will be withdrawn from the study: change in neurological examination, sustained change in intracranial pressure, blood pressure, heart rate, or oxygen saturation that is outside of provider-prescribed range, significant pain exacerbated by mobilization.^{22,34}

g. Description of what happens to participants receiving therapy when study ends or if a participant's participation in the study ends prematurely.

Upon study procedure completion participants will continue to receive usual care.

4. Inclusion/Exclusion Criteria

Inclusion criteria:	Rationale:
Age \geq 18 years	Spontaneous intracerebral hemorrhage and acute ischemic stroke is typically a disease of the adult.
Supratentorial intracerebral hemorrhage with or without intraventricular hemorrhage	Only patients with a supratentorial ICH will be included due to the fact that patients with infratentorial ICH often require surgery, introducing an overlay of inflammation above that which is caused by the ICH itself. It is known that intraventricular hemorrhage increases severity of illness and mortality, however it is a common co-occurring process in patients with ICH and should be studied concurrently. ¹³
Acute ischemic stroke with a Medical Research Council Sum Score (MRCSS) of <27.	Patients with a clinical diagnosis of stroke and motor weakness as identified by the MRCSS as less than 27. ²¹
Pre-morbid modified Rankin Score of 0-2	The modified Rankin Score (mRS) is a commonly

	used tool to quantify disability after stroke and is scored from 0 to 6 with higher scores describing increased disability including death. The mRS will be used to characterize a patient's pre-morbid functional status correlating with a patient's potential for recovery after stroke as well as an outcome measure at discharge and 30 days after hemorrhage. ^{5,13} Patients with a mRS >2 prior to admission have poor potential for recovery.
Patient must be able to provide informed consent or have a legally authorized representative to provide consent on their behalf	
Exclusion criteria:	

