a. Primary outcome variable.

Pro-inflammatory cytokines: IL-1 β , TNF α , IL-6; Anti-inflammatory/repair factors: IL-10, BDNF

b. Secondary outcome variables will be measured at discharge and 30 days post-intracerebral hemorrhage or acute ischemic stroke.

- Modified Rankin Scale (mRS)
- Barthel Index will be measured at discharge and 30 days
- Medical Research Council Sum Score and dynamometry to measure muscle strength
- Discharge location (e.g., home, nursing facility), although not well studied, is commonly associated with physical function at discharge.
- SF-12
- Vital signs (e.g., heart, rate, blood pressure, respiratory rate)
- Delirium positive days
- Hospital acquired infections (e.g., catheter associated urinary tract infection and central line associated blood stream infection)
- CSF cytokines and repair factors
- Stroke Impact Survey

c. Statistical plan including sample size justification and interim data analysis.

Sample size was calculated for a fully powered trial and 9% of this sample size will be used for this pilot according to Cocks' methodology.¹⁰ An effect size of 0.28 was used, based on a published single group observational study in critically ill patients with a primary outcome of cytokine change.⁴⁷ Detection of an effect size of 0.28 with power of 80% and an α of 0.05 requires a sample size of 400 for a full trial and 9% represents a pilot sample size of 36 participants. Due to the enrollment of two stroke phenotypes, ischemic and hemorrhagic, we will analyze each cohort separately, therefore 40 participants per cohort are required. Accounting for attrition, up to 100 participants may be consented in order to enroll up to 40 participants per cohort. Each cohort will have 20 participants in each of two arms, intervention and control. It is estimated that at least 3-5 patients will be enrolled per month over 18 months.

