Descriptive statistics will be used to report sociodemographic variables. Baseline characteristics will be compared between the two groups. If they are found to be similar, post-intervention outcomes will be compared between the groups. If the baseline characteristics are found to be different, an adjusted analysis as described below will be conducted. Mean (SD) or median (IQR) will be used to describe continuous variables, and frequency (%) will be used for categorical variables. Mean differences in cytokines between the three time points (baseline, day 3 and day 7) will be calculated for each participant in the intervention and control groups. We will also plot data over time by group. Assumptions of normality will be checked and appropriate parametric or non-parametric tests will be used to detect absolute mean differences due to the small sample size, with an a priori significance level of 0.05, although the primary aim of this study is to estimate effect size. Data quality will be ensured by analyzing all samples in duplicate and procurement of samples will be performed by the same investigator. Statistical analysis will be performed using Stata 14.0 (College Station, Texas).

Primary aim (1): To determine whether a regimen of twice daily 20-minute sessions of CE plus usual care administered to patients with sICH and AIS (n=20) increases cytokines of the M2 phenotype and decreases cytokines of the M1 phenotype within 10 days of sICH when compared to a similar group of patients with sICH receiving usual care only (n=20).

The effect size, absolute difference between the two groups and the standard error of the difference will be estimated. The standardized difference will be estimated using Cohen's d. A two-sample t-test will be used to detect differences between post-test outcomes. If the baseline outcome is different, an analysis of covariance (ANCOVA) will be used to compare the outcomes between the two groups adjusting for the baseline difference as a covariate.

Hypothesis: Patients in the CE group will demonstrate an increase in cytokines of the M2 phenotype and a decrease in the M1 phenotype when compared to the group receiving usual care only.

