Aim 2: To determine the effects of twice-daily, lower extremity CE of 20 minutes duration plus usual care compared to usual care alone and a third retrospective cohort of patients receiving usual care during the COVID-19 pandemic on, the immediate and sustained physical impairment and disability scores at NCCU discharge and 30 days after hemorrhage.

Data from this aim will be analyzed in the same fashion as described above.

Hypothesis: The CE group will demonstrate decreases in 90-day modified Rankin Scale score, increases in the Medical Research Council sum score (muscle strength) and grip strength, less delirium positive days and hospital acquired infections.

d. Early stopping rules.

If a patient meets the following stopping criteria on >2 consecutive sessions the patient will be withdrawn from the study: change in neurological examination, sustained change in intracranial pressure, blood pressure, heart rate, or oxygen saturation that is outside of provider-prescribed range or significant pain exacerbated by mobilization.

6. Risks

a. Medical risks, listing all procedures, their major and minor risks and expected frequency.

The risks of this study are designed to be minimal. Potential risks to the participant include the following: hemodynamic instability, increased intracranial pressure, skin breakdown associated with the supine cycle ergometer, pain, muscle spasm and musculoskeletal injury.

b. Steps taken to minimize the risks.

Patients are continuously monitored on a cardiorespiratory monitor with oxygen saturation, heart rate, intracranial pressure (when applicable) and blood pressure, measured by arterial catheter or non-invasive cuff. Blood pressure, heart rate, oxygen saturation, respiratory rate and intracranial pressure will be measured and recorded continuously using the Medical Informatics, Sickbay software application currently installed in the NCCU and collecting data from all cardiorespiratory monitors. Pain will be measured and documented every 5 minutes visual analog scale or behavioral pain scale in patients unable to report pain level.

The NCCU is staffed 24 hours per day by a dedicated team of Neuro Intensivists, fellows and resident physicians assigned exclusively to the unit who can respond immediately to physiologic changes or adverse events when notified. A chain of command is followed when a primary provider is not available to respond due to other emergent patient care duties.

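### SF-12 is never collected, and the baseline-outcome ANCOVA that Aim 2 inherits has no baseline for Barthel and apparently only a pre-stroke one for mRS

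*Combined protocol and SAP*

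**What the plan says.** Study Statistics, item b, opens its list with "Secondary outcome variables will be measured at discharge and 30 days post-intracerebral hemorrhage or acute ischemic stroke". The list includes mRS, Barthel, MRC sum score with dynamometry, SF-12 and the Stroke Impact Survey.

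Section 3a describes two questionnaires. After enrollment, the PROMIS Global "questionnaire for (pre-morbid health) will be administered to the patient or their LAR depending on the patient's ability to complete the form". Then, "At the last follow-up visit the patient or LAR will complete the Stroke Impact Survey". Table 1 has the same two rows: PROMIS on study day 1 and the Stroke Impact Survey at 30 days.

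In Table 1 the row "Modified Rankin scale score" is marked at admission day 1–2, at ICU transfer and at 30 days. Section 4 says "The mRS will be used to characterize a patient's pre-morbid functional status", requires a value of 0–2 for entry, and then uses the scale as an outcome. Section 3b adds a 90-day mRS by telephone, recorded for all patients.

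Study Statistics, item c, sets a two-sample t-test on post-treatment values for the primary aim. It continues: "If the baseline outcome is different, an analysis of covariance (ANCOVA) will be used". Earlier in item c a broader sentence calls for an adjusted analysis if baseline characteristics differ. For Aim 2 the plan says only: "Data from this aim will be analyzed in the same fashion as described above".

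**The concern.** There are two faults of different weight.

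The first is one of consistency. One named secondary outcome has no scheduled collection, and a second is given two time points in one place and one in another. Followed as written, SF-12 returns no data.

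The second concerns the analysis. Aim 2 is about physical impairment and disability, and the 90-day mRS stands first in its hypothesis. For patients without an in-person visit, section 3b makes that score the only follow-up outcome. The rule for deciding whether to adjust refers to the baseline value of the outcome. If a scale has no post-stroke baseline, the rule gives no instruction, or it looks at a quantity that says little about how severe the stroke was. Whoever runs the analysis must then choose a covariate, or none, after seeing the data. With 20 patients per arm in each stroke cohort, that choice can move the estimate, and estimating an effect size is this pilot's stated primary aim.

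**Working it through.** **Step 1: scheduling.** SF-12 appears once, in the outcome list. It has no row in Table 1 and is not in the section 3a procedures, so 0 of its 2 stated assessments are scheduled. The Stroke Impact Survey has 1 of the 2 assessments that the list implies.

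**Step 2: which Aim 2 scales have a baseline of their own.** From Table 1, with the 90-day mRS from section 3b:

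| Outcome | Before or at study day 1 | Later | Own-baseline check |
|---|---|---|---|
| Barthel | none | ICU transfer, 30 days | impossible |
| mRS | admission day 1–2, not labelled | ICU transfer, 30 days, 90 days | pre-stroke state only, if the admission value is pre-morbid |
| MRC sum score | study day 1 | study days 3 and 7, ICU transfer, 30 days | possible |
| Grip strength | study day 1 | study days 3 and 7, ICU transfer, 30 days | possible |

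The admission mRS sits in the screening column, and section 4 gives the scale only two uses: pre-morbid status for eligibility, then outcome. Pre-morbid is therefore the natural reading, but it is an inference.

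**Step 3: does the broader trigger fill the gap?** It points to an adjusted analysis described later in item c. The only adjusted model there is the ANCOVA on the baseline difference. No severity covariate is named, so adjustment is permitted but not defined for mRS and Barthel.

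**Step 4: what adjustment could be worth.** The plan's own sizing first. For an effect size of 0.28, 80% power and α 0.05 (taken as two-sided), n per arm = 2(1.960 + 0.8416)²/0.28² = 200.2, rounded up to 201. That is 402 in total against the stated 400, and 9% of 400 = 36, which the plan raises to 40 per cohort (20 per arm). These figures are not in dispute.

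In a linear model, adjusting for a covariate with correlation r to the outcome multiplies residual variance by 1 − r². The standard error of the group difference, in outcome SDs, is then √[(2/20)(1 − r²)]. The documents give no r; 0.5 is assumed, with a range of 0.3 to 0.7.

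| r | 1 − r² | Variance reduction | SE of difference (SD) |
|---|---|---|---|
| 0 (no adjustment) | 1.00 | 0% | 0.316 |
| 0.3 | 0.91 | 9% | 0.302 |
| 0.5 | 0.75 | 25% | 0.274 |
| 0.7 | 0.51 | 49% | 0.226 |

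One covariate costs one residual degree of freedom: 40 − 2 = 38 becomes 37. As mRS is ordinal, the table is only a guide for that scale.

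**The case against.** A reader might infer that Aim 2's baseline-adjusted analysis cannot be run on its main outcomes. The documents do not support that. MRC sum score and grip strength are named in the Aim 2 hypothesis and have a study-day-1 baseline in Table 1. Barthel and SF-12 are not named in that hypothesis. The default t-test needs no baseline at all.

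A reader might also infer that any chance imbalance in severity would pass unchecked into the disability comparison. That is not established either. Item c compares baseline characteristics and allows adjustment when they differ, and section 3a extracts hematoma volume and edema from routine CT. In the randomised comparison, chance imbalance is also already reflected in the standard error.

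Nor is it an error that no quality-of-life questionnaire is given twice. PROMIS serves the objective on pre-morbid function and quality of life, and the Stroke Impact Survey covers follow-up. Repeating PROMIS would be a preference.

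Two further objections have force. If the admission mRS is a current score, the mRS part of this point falls. And the candidate covariates are imperfect: the ischemic cohort is restricted to MRC sum scores below 27, GCS has no row in Table 1, and section 3a words strength testing differently from Table 1.

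What stands after all this is that the adjustment rule is undefined for Barthel and close to uninformative for mRS, and that no covariate is named in its place.

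**Conclusion.** The point holds in limited form. The SF-12 and Stroke Impact Survey entries are conflicts of wording that must be reconciled. The rule inherited by Aim 2 cannot be applied to Barthel. For mRS it would test only the pre-stroke state, on the reading that the admission value is pre-morbid. For MRC sum score and grip strength it works.

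Adjustment is therefore not impossible: usable data exist, but the plan does not say which to use. The gain from naming a covariate is a variance reduction of 25% (9% to 49%) against no adjustment. This rests wholly on the assumed correlation, and restricted range may put it at the lower end. The gain over what the plan already permits would be smaller when its conditional adjustment happens to be used. The firmer benefit is that the model for the disability scales is fixed before the data are seen.

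**What to change.** 1. For mRS (ICU transfer, 30 days and 90 days) and Barthel, replace the conditional baseline-outcome ANCOVA with an adjustment that is always made, within each stroke cohort, for a pre-specified early severity covariate. Candidates already obtained are the study-day-1 MRC sum score where testable, the GCS at 48 hours used for eligibility, or both. Baseline hematoma volume is an option in the hemorrhage cohort. State how a missing covariate is handled. For the comparison with the retrospective pandemic cohort, the covariate must be one that the charts record.
2. Label the admission mRS in Table 1 as pre-morbid or current.
3. Delete SF-12 from the secondary outcomes, and state that the Stroke Impact Survey is given at 30 days only.
4. Reconcile section 3a, which describes strength testing on days three and seven for the control group, with Table 1, which has it on study days 1, 3 and 7 for both groups. Confirm that the day-1 score precedes the first cycling session.

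The cost is wording, plus carrying GCS from screening into the dataset. The downside is that the MRC sum score will be missing in patients who cannot follow commands and is restricted in range in the ischemic cohort, so its value as a covariate may be modest there. No new visit or instrument is needed.

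### The cytokine test depends on an unspecified normality check while the effect measure stays the absolute difference and Cohen's d, so the test and the reported effect can describe different quantities

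*Combined protocol and SAP*

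**What the plan says.** All of this is in the combined protocol and SAP, Study Statistics.

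- **Primary variables (item a).** There are five: IL-1β, TNF-α, IL-6, IL-10 and BDNF.
- **Size (item c).** The ischemic and hemorrhagic cohorts are analysed separately: "Each cohort will have 20 participants in each of two arms, intervention and control". The full-trial basis is "An effect size of 0.28 was used, based on a published single group observational study in critically ill patients", which "requires a sample size of 400 for a full trial"; then "9% represents a pilot sample size of 36 participants".
- **General analysis paragraph (item c).** "Assumptions of normality will be checked and appropriate parametric or non-parametric tests will be used to detect absolute mean differences", "with an a priori significance level of 0.05". The same sentence says that estimating the effect size is the main purpose. Continuous variables may be described by mean (SD) or by median (IQR), and differences between baseline, day 3 and day 7 are calculated for each participant.
- **Primary aim (1).** The plan reports the absolute group difference with its standard error. "The standardized difference will be estimated using" Cohen's d. The comparison is a two-sample t-test on post-test values, replaced by ANCOVA if the baseline outcome differs.

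The plan does not say which normality diagnostic applies, at what cut-off, or whether the decision is made per marker, time point or cohort. It mentions no transformation. It names no effect measure for use when a non-parametric test is chosen.

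**The concern.** Two instructions cover the same primary comparison. One lets the data choose between a parametric and a non-parametric test. The other names a t-test outright. An analyst cannot follow both when normality fails.

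The effect measures do not switch with the test. A rank test does not estimate a mean difference or Cohen's d, although the plan says that non-parametric tests will detect absolute mean differences. A marker that fails the check would therefore carry a rank-based p-value beside a mean-based effect size. With five markers, two cohorts and several time points, the choice could fall differently from one result to the next, and the effect sizes would not share a defined scale.

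In a confirmatory trial this would be an untidy specification. Here it affects the main product, because the pilot is meant to supply an effect size. If concentrations are right-skewed, the scale on which d is computed changes its value.

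**Working it through.** **1. The plan's own figure.** Inputs from item c: d = 0.28, power 80%, α = 0.05. Sidedness is not stated; I take two-sided.

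n per arm = 2(z₀.₉₇₅ + z₀.₈₀)²/d² = 2 × (1.960 + 0.842)²/0.28² = 2 × 7.849/0.0784 = 200.2, so 201 per arm and 402 in total, against 400 stated. 0.09 × 400 = 36. The sample-size figures reproduce and are not in question here.

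**2. The sentences side by side.**

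| Situation | Test under the general paragraph | Test under Primary aim (1) | Effect reported |
|---|---|---|---|
| Normality accepted | parametric | t-test | absolute difference, d |
| Normality rejected | non-parametric | t-test | absolute difference, d |

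The second row holds the contradiction about the test. If the general paragraph governs, it also holds the mismatch between test and effect. Neither depends on any assumption about the data.

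**3. How far the scale can move d.** The documents give no SD, CV or shape for any marker, so this step is conditional. Assume lognormal values with the same log-SD s in both arms and a log-scale standardised effect δ:

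raw d = (e^{δs} − 1) / √[(e^{s²} − 1)(1 + e^{2δs})/2]

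At δ = 0.28, s = 1.0: 0.3231/√(1.7183 × 1.3753) = 0.3231/1.5373 = 0.210.

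| log-SD s | Population raw d | Below 0.28 by | Mean estimated raw d, 20 per arm (simulated) |
|---|---|---|---|
| 0.5 | 0.262 | 7% | about 0.27 |
| 0.8 | 0.234 | 16% | about 0.25 |
| 1.0 | 0.210 | 25% | 0.23 to 0.24 |
| 1.3 | 0.169 | 40% | 0.21 to 0.22 |

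The mean log-scale estimate at 20 per arm is 0.28 to 0.29. The sampling SD of d is about √(2/20) = 0.32, so the 95% half-width is about 1.96 × 0.316 = 0.62. The average gap between scales is at most about 0.08.

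**4. Direction.** Let log-spread differ between arms.

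- Control 1.0, treated 1.2, a rise of 0.28 log units. Log d = 0.28/√[(1 + 1.44)/2] = 0.25. The raw means are e^{0.5} = 1.649 and e^{0.28+0.72} = 2.718, and the raw variances are 4.67 and 23.80. Raw d = 1.070/√14.23 = 0.28.
- Control 1.0, treated 0.8, a fall of 0.28 log units. Log d = −0.31 and raw d = −0.36.

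In both cases raw d is the larger.

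**5. Power at 20 per arm, log-scale effect 0.9 (simulated).** The switch is modelled as Shapiro-Wilk at 5% in each arm, with Mann-Whitney if either fails. That diagnostic is my assumption.

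| log-SD | Raw t-test always | Normality switch | t-test on logs |
|---|---|---|---|
| 0.8 | 66–67% | 76–79% | 78–81% |
| 1.0 | 60–61% | 76–79% | 78–81% |
| 1.3 | 48–49% | 76–79% | 78–81% |

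Ranges cover repeat simulations. Within a run the switch loses about 2 points against the log t-test (1 to 3 across runs). Both arms pass the check in under 3% of trials at these log-SDs. The type I error of the switch was 4.5% to 5.7% over log-SD 0.25 to 1.5.

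**The case against.** The strongest reply is that the plan already guards against skewness. It checks normality and moves to a non-parametric test, and step 5 shows that this rule keeps nearly all the power and holds the type I error. That stands. The large power loss arises only if the unconditional t-test sentence overrides the check, which the text leaves open.

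A reader might infer that raw Cohen's d is always too small. The documents do not support this. They neither say that the markers are skewed nor give any spread. The shortfall needs roughly lognormal data with similar log-SD in both arms, it is slight at low log-SD, and it reverses in the cases of step 4.

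A reader might also infer that the next trial's sample size would be inflated. That does not follow either. Raw d is the right planning input for a later trial analysed by a raw t-test. The resulting N is too large only if that trial is analysed on logs, and no document says how it will be analysed.

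It is also fair to say that at 20 per arm, sampling error in d dwarfs the scale effect. That limits the numerical harm in any single estimate. It does not settle which quantity is being estimated, and it does not remove the conflict between the two test instructions. Nor is the log scale the only defensible choice; the essential requirement is one scale, fixed in advance, with a matching test and effect measure.

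**Conclusion.** The point holds as a gap in specification. The plan gives two incompatible rules for choosing the primary test and no effect measure to match one of them, in a pilot whose stated purpose is an effect size. This rests on the text alone.

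Its numerical size is conditional. With lognormal markers and equal log-SD between 0.5 and 1.3, a log-scale effect of 0.28 is a raw population d of about 0.26 down to 0.17. The average pilot estimate would be about 0.27 down to 0.21, against a sampling SD of about 0.32. Power at a log-scale effect of 0.9 is lowered materially, to about 66%, 61% or 49% at log-SD 0.8, 1.0 or 1.3, only if the raw t-test is run regardless of the check.

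The plan should be changed because the remedy is nearly free. The documents do not show that its estimates will be wrong in a known direction.

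**What to change.** In Study Statistics, item c and Primary aim (1), replace the normality-triggered choice with one stated analysis:

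- log-transform concentrations of all five primary markers;
- compare arms by one baseline-adjusted model on that scale, in every case, instead of moving between a t-test and ANCOVA according to the baseline result;
- report geometric mean ratios with 95% CIs, and compute the standardised difference on the log scale;
- express within-participant changes as log ratios, since raw differences can be negative and cannot be logged;
- keep a rank test as a sensitivity analysis only;
- fix a substitution rule for zero or below-limit values before any are logged.

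The cost is a short amendment to the text, with no new data and no added patient burden. The small downside is that effects are read as ratios instead of absolute differences, and the substitution rule must be settled in advance.
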